4.0 INCLUSION/EXCLUSION CRITERIA

Inclusion criteria for psychosis subjects

1. Men and women age 18 - 65.
2. Communicative in English.
3. Provide voluntary, written informed consent.
4. Physically healthy by medical history.
5. BMI > 17.5 and < 45.
6. Diagnosis of a psychotic disorder confirmed by Structured Clinical Interview for DSM-V (SCID) or diagnostic interview with a trained clinician.
7. Stable medication regimen over at least the past two weeks, including the use of either an oral or intramuscular administration of an antipsychotic medication.

8. For females, no longer of child-bearing potential, or agreeing to practice effective contraception during the study (e.g., established use of oral, injected or implanted hormonal methods of contraception; placement of an intrauterine device [IUD] or intrauterine system [IUS]; barrier methods: condom with spermicidal foam/gel/film/cream/suppository or occlusive cap [diaphragm or cervical/vault caps] with spermicidal foam/gel/film/cream/suppository; male partner sterilization; or true abstinence when this is in line with the preferred and usual lifestyle of the subject); and,
9. For females of child-bearing potential, must have a negative urine pregnancy test before MRI and drug administration.
10. Not breastfeeding/nursing at time of screening or at any time during the study.

Exclusion criteria for psychosis subjects

1. Age less than 18 or greater than 65.
2. Not communicative in English.
3. Unable to provide written informed consent.
4. Current medical or neurological illness.
5. History of severe head trauma.
6. BMI < 17.5 or > 45.
7. Meets criteria for diagnosis of substance or alcohol use disorder within the past month.
8. Positive urine pregnancy test during the study.
9. Breastfeeding/nursing at time of screening or at any time during the study.
10. Conditions that preclude MR scanning (as defined in the Screening Form)
11. Conditions that preclude study drug administration (as defined in the Screening Form)

Inclusion criteria for healthy controls

All of the above except for subjects will be psychiatrically healthy and not taking psychotropic or potentially psychoactive prescription medication.

Exclusion criteria for healthy controls

All of the above and in addition:

1. Current use of psychotropic or potentially psychoactive prescription medication.

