5.0 ENROLLMENT

5.1. Recruitment: Study participants will be recruited from the **Psychiatric Genotype/Phenotype Repository (PGPR, IRB #080606)**: The PGPR study includes a clinical interview during which diagnostic and clinical history data is collected. At the end of this interview, individuals will be asked by one of the key research personnel listed on this application if they are interested in participating in the study. The PI of this study is the same PI for the PGPR study. Subjects will be read a script describing the study. Subjects will be told that the study is separate from their participation in the PGPR study and choosing not to participate in the study will not affect their participation in the PGPR study. In addition, individuals that have previously completed the PGPR study may be contacted and asked if they would like to participate in the study. The consent form for the PGPR study states that subjects may be contacted and asked if they would like to take part in future studies, if they agree. Subjects will be read a script telling them about the study. The telephone screening form used for the Psychiatric Genotype/Phenotype study will be re-administered to make sure that they still meet the original criteria for participating in the Psychiatric Genotype/Phenotype Study (i.e. age, physical health, and MRI requirements).

We will make every effort to recruit equal numbers of men and women. We will not exclude subjects based on gender or minority status. We minimize coercion throughout the study by repeatedly informing subjects that

they may discontinue study procedures at any point, or opt-out of any specific part of the study they become uncomfortable with completing.

We plan to recruit up to 80 subjects (up to 40 healthy control subjects and up to 40 patients with psychotic disorders) for the study. We hope to acquire analyzable data from at least 20 control subjects and 20 patients.

Subjects who were recently recruited in other psychiatry studies also conducted by this PI (e.g. genotype/phenotype studies) may not be required to participate in components of this study that would duplicate efforts (e.g. SCID interview). We plan to include data from those studies in the analyses of data from this study. Participants will be compensated for all activities they complete.

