6.4.b Scanning Procedures: Imaging studies will take place on a Phillips 3.0 T MRI scanner. The magnet and the magnet's control console are in separate rooms, but the investigator and the subject will be in voice communication at all times, and the investigator will be able to see the subject through a window. All data acquired on the scanner will be securely transferred over the Vanderbilt network to the Institute of Imaging Science's server. Imaging data will be de-identified and only be accessible to the PI, co-investigators, and VUIIS personnel. Scanning procedures may include: 1) Structural imaging, 2) Resting state functional imaging, 3) ASL imaging to non-invasively measure cerebral blood flow, and 4) Functional imaging with task – while in the scanner, participants will view images that include faces, objects and scenes. Images are projected to a mirror above the participants head from a projector located outside the scanner room. Some runs will repeat the same face or object, some runs will present different images. Participants will complete between 1-8 runs of this task. To maximize participant's attention to the images, participants will be instructed to push a button to detect targets. Targets may include image repeats or changes in the image (e.g., image size). This task is similar to the one reported in McHugo et al., 2019.

6.5 Study Drug Administration: During Visit 2, participants will be randomly assigned to an intervention arm in which they will receive two 250mg LEV capsules or two placebo capsules. Both the participant and the research team will be blinded to which arm each participant is in. During Visit 3, the participant will undergo cross-over and receive either two 250mg LEV capsules or two placebo capsules (whichever intervention they did not receive in Visit 2).

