11.0 STATISTICAL CONSIDERATIONS

11.1 Data Management: All study data will be stored in a REDCap study database. The exception is for the raw and processed MRI scans that will be stored in the Vanderbilt XNAT Image Database system.

11.2 Statistical Analyses:

11.2.a. Drug levels: We will collect serum drug levels at the time of imaging to create a dose-response curve. The response will be defined as the change of a specific measure (hippocampal activity) from baseline. We will utilize nonlinear regression methods to create curves. Many studies have established a dose-response curve for epilepsy efficacy and safety (Boon et al., 2002; Meencke and Buyle, 2006; Rhee et al., 2017), but no dose-response curve currently exists for other measures such as imaging markers.

11.2.b. Clinical Data: The data will be used to better characterize the patients enrolled in this study.

11.2.c. Imaging Data: All images will be converted to an analyzable format. Spatial preprocessing will be performed using SPM5 (Functional Imaging Laboratory, London, UK) and FSL software (Analysis Group, FMRIB, Oxford, UK) or other comparable software. This will allow for realignment and transformation into a standardized space. Pairwise subtractions will then be performed, yielding images of mean difference and standard deviation, which can be used to produce z-scores and statistical parametric maps (SPMs). Statistical parametric maps will be constructed using a mixed effects model (subjects are considered random effects, conditions are considered fixed effects). SPM or other comparable software will allow us to test for condition effects, group effects, and group-by-condition interactions. Duration of illness and treatment will be assessed as confounding variables using an analysis of covariance. The duration of illness will be added into the fixed effects statistical model for the within group analysis as a covariate. Alternative methods will be employed when the data suggest a

more appropriate method. The effects of duration of illness and treatment on structural imaging data will be assessed by correlation analysis.

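### Illness duration is to be correlated with brain structure in patients aged 18 to 65 with no age adjustment specified, so an association could not be separated from normal ageing

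*Combined protocol and SAP*

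**What the plan says.** Section 11.2.c deals with the structural scans in one sentence: "The effects of duration of illness and treatment on structural imaging data will be assessed by correlation analysis". It does not say whether the correlation is simple or partial, and it names no structural measure and no covariate.

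The rest of section 11.2.c does not supply an age term:

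- On confounding: "Duration of illness and treatment will be assessed as confounding variables using an analysis of covariance".
- On the within-group model: "The duration of illness will be added into the fixed effects statistical model for the within group analysis as a covariate".
- Just before the structural sentence is a general reservation, "Alternative methods will be employed when the data suggest a" better-suited approach. It names no method, covariate or trigger.

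The age criterion in section 4.0 is "Men and women age 18 - 65", and controls inherit it. No age matching of the groups is described. On numbers, section 5.1 plans "up to 40 patients with psychotic disorders" and adds: "We hope to acquire analyzable data from at least 20 control subjects and 20 patients". Section 6.4.b lists the structural scan as optional: "Scanning procedures may include: 1) Structural imaging". It plays no part in Hypotheses 1–3.

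**The concern.** Duration of illness is an arithmetic function of age: duration = age − age at onset. When ages may span 47 years and onset falls in a much narrower band, most of the spread in duration is spread in age. Any structural measure that changes with normal ageing will then correlate with duration even if illness does nothing. The section speaks of *effects* of duration, so a significant coefficient invites a causal reading that the analysis cannot support.

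The same problem arises for *treatment* if the word means how long a patient has been treated, because that also grows with age. The text does not define the word.

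At stake is the interpretation of one secondary, observational analysis. The levetiracetam comparison does not depend on it.

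**Working it through.** **Plan's own figure.** None exists for this analysis. The 80.3% power in section 11.3 concerns change in hippocampal activity and has no bearing here.

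**Inputs from the documents.** Age range 18–65 (section 4.0). Patients: at least 20 hoped for, at most 40 (section 5.1). Alpha 0.05 (section 11.3; sidedness not stated, two-sided used here).

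**Assumed inputs, not in the documents.** Age uniform over 18–65. Onset mean 22 (SD 5) or mean 25 (SD 8), held between 12 and current age. Correlation of age with the structural measure 0, −0.2, −0.3 or −0.4. True effect of illness duration: none.

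**Step 1: age–duration correlation.** With duration = age − onset, this comes out at about 0.94 (onset SD 5) and 0.87 (onset SD 8).

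**Step 2: spurious correlation.** With no illness effect, the expected duration–structure correlation is about (age–duration) × (age–structure).

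- Smallest case: 0.87 × −0.2 = −0.174
- Largest case: 0.94 × −0.4 = −0.376

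**Step 3: size needed for significance.** Critical |r| = t / √(t² + n − 2).

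- n = 20: t = 2.101, so 2.101 / √(4.414 + 18) = 0.444
- n = 40: t = 2.024, so 2.024 / √(4.098 + 38) = 0.312

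**Step 4: false-positive rate, hand check of the largest case** (Fisher z, standard error 1/√(n − 3)).

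- n = 20: (atanh 0.444 − atanh 0.376) × √17 = (0.477 − 0.395) × 4.123 ≈ 0.34, upper tail about 37%
- n = 40: (0.323 − 0.395) × √37 ≈ −0.44, upper tail about 67%

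**Step 5: simulation, 20,000 samples per cell.** Share of samples in which the unadjusted correlation is significant:

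| Onset mean (SD) | Age–structure r | n = 20 | n = 40 |
|---|---|---|---|
| 22 (5) | 0 | 4.6% | 4.9% |
| 22 (5) | −0.2 | 12.5% | 21.3% |
| 22 (5) | −0.3 | 23.0% | 43.2% |
| 22 (5) | −0.4 | 38.7% | 69.1% |
| 25 (8) | 0 | 4.9% | 5.0% |
| 25 (8) | −0.2 | 11.2% | 19.1% |
| 25 (8) | −0.3 | 20.0% | 37.5% |
| 25 (8) | −0.4 | 32.9% | 61.9% |

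Other ways of truncating implausible onset ages move these figures by up to about three points. Across them the ranges are 11–39% at 20 patients and 18–69% at 40. The partial correlation given age is significant in about 5% of samples in every cell.

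**Step 6: narrower ages.** If recruited ages run only from 18 to 35 (onset mean 24, SD 4 or 8), the age–duration correlation falls to 0.51–0.73. For age–structure correlations of −0.2 to −0.5, the unadjusted rate is 7–37% at n = 20 and 10–67% at n = 40. The problem shrinks but remains.

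**Step 7: price of adjusting.** The standard error of the duration coefficient grows by about 1/√(1 − r²), where r is the age–duration correlation.

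- r = 0.87: 1/√(1 − 0.757) = 2.0
- r = 0.94: 1/√(1 − 0.884) = 2.9

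**The case against.** The case against has five parts.

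- **Under-specified rather than wrong.** The words used do not exclude a partial correlation, and the plan reserves the right to other methods. This stands to the extent that a reader should not infer that the plan has chosen to ignore age. But a plan that names no covariate has not planned age adjustment, and the reservation is too vague to supply it.
- **A false finding is not inevitable.** A reader might infer that ageing will be reported as an illness effect. The documents do not support that. At 20 patients, 61–89% of the simulated samples under the main assumptions give no significant result, and there is no inflation if the measure does not vary with age. The sound claim is that such a finding can be reported and could not be told apart from ageing.
- **Treatment may not be confounded.** A reader might extend the point to *treatment* without qualification. If the word means levetiracetam against placebo, each patient is his or her own control about a week apart, and age cannot confound the contrast. Prior treatment is the more natural reading, since the word is paired with illness duration as a confounder and patients must be on an antipsychotic. The text does not settle it.
- **Little rides on it.** Correct. The scan is optional and outside the three hypotheses. An inference that the main result is at risk would be unfounded.
- **The remedy leaves a weak analysis.** Largely correct. With 20 to 40 patients and a standard error two to three times larger, the adjusted estimate will be imprecise. That imprecision reflects what the data can say about duration apart from age. The tighter unadjusted interval answers a different question.

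**Conclusion.** The point holds for illness duration, as a gap in a secondary analysis that should be closed. As written, section 11.2.c gives no means of separating illness duration from age in patients who may be 18 to 65. Under the assumed inputs and no illness effect, the false-positive rate is about 11–39% at 20 patients and 18–69% at 40, instead of 5%. More patients make it worse, because the bias does not shrink as the sample grows.

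The size rests on three things the documents do not give: the realised age spread, the spread of onset age, and how strongly the chosen measure varies with age. The direction does not depend on the exact values, provided structure varies with age at all. For *treatment* the point is conditional on the word meaning duration of prior treatment. Hypotheses 1–3 and the primary aim are untouched.

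**What to change.** In section 11.2.c:

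1. Replace the correlation with a regression, or partial correlation, of each named structural measure on illness duration, adjusted for age.
2. Define *treatment*. If it means duration of prior treatment, apply the same age adjustment.
3. Report the age–duration correlation next to the estimate and its confidence interval, and label the analysis exploratory.
4. Optionally, as a sensitivity analysis, estimate the age slope with controls included, stating the assumption that patients and controls share a common slope.

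The cost is a few sentences of analysis text and no new data: age is an eligibility criterion and is among the demographics listed in section 13.0. The real price is precision, since the standard error for duration will be roughly two to three times larger. With 20 to 40 patients the adjusted analysis may well be inconclusive, and the plan should say so in advance.

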12.0 PRIVACY/CONFIDENTIALITY ISSUES

The data files generated by the MRI scanner are coded using a project name and unique number generated sequentially. The scanner technicians will not have access to the key for this information. Image analysis will use the coded files. The safety surveys described above include questions about sensitive health issues. This information will remain with the signed consent form in a secured area near the scanner. Electronic databases containing identifiable subject information will be password encoded. Written information containing subject identifiers (informed consent, lab results, interview questionnaires, subject payment, etc.) will be stored in file cabinets in offices within the departments of Radiology and Psychiatry. Subjects will be assigned an alphanumeric code that will be used to label all research data including all questionnaires and MRI data.

13.0 FOLLOW-UP AND RECORD RETENTION

We anticipate participant recruitment and contact with subjects to be completed within one month. Study records will be maintained for at least two years after the study is closed with the IRB. In accordance with Vanderbilt guidelines, and as outlined to the subjects in the consent form, the subjects' confidentiality will be ensured throughout the study. Image data will be acquired by the 3 Tesla scanner and will be stored both on digital media (which will not leave the secured scanner area) and on Vanderbilt's secure REDCap database. The data may be maintained for an indefinite period of time since scientific progress may indicate that new analyses be carried out on previously obtained data. Future studies/analyses will be carried out with approval of the IRB. If paper records are to be destroyed those containing subject identifiers will be shredded directly or transferred to the hospital's shredding service. If electronic data containing subject identifiers is to be destroyed it will be disposed of using a medium-appropriate destruction method to prevent recovery. Data not containing subject identifiers will be disposed of by any convenient method.

In compliance with the National Institute of Health data sharing initiative, imaging data without any personal information attached may be shared with other investigators or public data repositories, which provides the research community with open access to datasets contributed by labs around the world. Information will be completely anonymized with demographics limited to age (accurate to the year up to 90 years old, or "90+" for older individuals), gender (male, female), group membership (e.g., disease/treatment state) and handedness. Data will be transferred using secure file transfer protocols.

